Remotely-Delivered Benefits Counseling for Service
Connection Applicants

NCT02677428

4/9/19

Project Description

1. Principal Investigator

[name]

2. Project Title

Remotely-Delivered Benefits Counseling for Service Connection Applicants

3. Purpose

The purpose of this study is to evaluate the utility of Remotely-Delivered Benefits Counseling in a 24-week clinical trial. This study will evaluate the effectiveness of Benefits Counseling on work and work-related outcomes with Veterans who are applying for service-connection. This study has the following specific aims and hypotheses:

Primary Aim 1: To estimate the effect of Remotely-Delivered Benefits Counseling on the slopes of paid work over time.

Hypothesis: The slopes of hours of paid work over time will differ between the control and Benefits Counseling groups, as evidenced by a significant, positive treatment-by-time interaction effect.

Exploratory Aim One: To estimate the effect of Remotely-Delivered Benefits Counseling on other outcomes.

Hypothesis: The slopes of hours of volunteer work; days attending school, days in vocational rehabilitation settings, days engaged in any one of the work-related activities; and income earned over time will differ between the control and Benefits Counseling groups.

Exploratory Aim Two: To conduct bivariate analyses of two of the components of mediation of Benefits Counseling's effects---correlation with the group assignment and with the outcome:

Hypothesis 2A: Assignment to Benefits Counseling (vs. control) will be associated with one or more of the following: (i) more positive changes in ratings of work's importance, (ii) greater decreases in beliefs that working and service connection are linked, and (iii) more positive changes in number of weeks attending any mental health or vocational counseling.

Hypothesis 2B: Individual slopes in hours worked over time will be associated with one or more of the potential mediators (i, ii, iii) as above in Hypothesis 2A.

4. Background

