Data collection will be conducted at the Northampton VA Medical Center and the West Haven VA Medical Center. Veterans will complete baseline evaluations, and then be given a user ID and instructions to log-on to a study website at home to receive their randomization assignment. Only those who do so will continue in the study and be asked to complete the telephone-delivered assessments on weeks 4, 12, and 24. This randomization after logging in restricts participation to people who demonstrate some motivation and ability to access a website.

Sequence of procedures for the clinical trial:

- Potentially eligible Veterans scheduled for a Compensation examination are identified by reviewing Compensation clinic schedules and charts.
- Potentially eligible Veteran receives letter explaining that a study recruitment telephone call will be coming, thus allowing the Veteran to opt out of receiving it (see Appendix). Veterans can also opt out by calling a toll-free phone provided in the letter.
- Telephone call inviting participation. The Research Assistant calls and asks the Veteran questions to determine eligibility. Following a script (see Appendix), the Research Assistant describes the study to the Veteran and schedules an appointment for informed consent and data collection. Appointments will be scheduled before a Veteran's planned Compensation examination and up to 3 months after the exam. Veterans vary in how able they are to schedule appointments immediately before or after Compensation examinations. Flexible scheduling balances feasibility and experimental rigor.
- Informed consent and baseline data collection by Research Assistant.
- The Research Assistant gives the Veteran a user ID and password to log on to the study Website.
- Veteran goes home, logs onto the website, and receives directions to log-on to either the Benefits Counseling or Control websites (i.e. the Veteran is randomized).
- Veteran is called by the study therapist within two days of logging on and is counseled with the assigned treatment. If the Veteran has not logged on for randomization within a week, then the therapist will call and encourage the Veteran to log-on for randomization and continuation in the study. If after one more week the Veteran has not been randomized, that participant will be discontinued from the study.
- Assessments by phone at weeks 4, 12, 24 (only of randomized Veterans).

B. Remotely-Delivered Benefits Counseling

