1. Integration of Website Use and Therapist Phone Calls:

- a. Purposes of Phone Calls:* The purpose of the Benefits Counseling phone calls is to complement the web-based modules and to support the Veteran in applying the website content to his/her particular situation.
- b. Introduction:* The therapist explains that his/her role is to help the Veteran get as much as possible out of the Benefits Counseling website. The therapist plans the dates and times for phone calls and provides the Veteran with a phone number to call him/her for rescheduling or brief questions.
- c. Timing and Content of Session Calls:* The therapist tries to schedule calls soon after the Veteran has completed each of the first two modules. At each of the calls, the therapist makes general inquiries about the Veteran's experience using the site, the information covered, and any follow-up the Veteran plans. Based on these responses, the therapist

will follow-up with questions about the content of the module just completed (domains described below).

d. Timing and Content of Session-Three Call: Therapists will instruct Veterans to complete Module Three after receiving their service-connection decision and to call after completing it. If the Veteran has not called by week 12, the therapist will call the Veteran to determine the status of the C&P claim, and module completion. If the C&P decision has not been received, the therapist will call again at 16 and 20 weeks to review the decision and module, if the Veteran hasn't called first.

e. Overall Call Limit: Therapists will limit calls to no more than 30 minutes each, and no more than three therapy calls per Veteran; calls lasting fewer than five minutes (e.g. for scheduling or brief questions) will not count towards the three call limit.

2. Website

a. The VACHS IRB reviewed the website's content as part of protocol MR0031, IRB #01389, for preliminary use by Veterans. Screenshots of the website are attached as an Appendix.

The website can also be accessed by

Going to vabenefitseducation.org
 Entering username [name]
 Password bluefish
 Selecting go to cloned interview.

b. The Goals and Content of the Three Modules: In keeping with published literature and our pilot experience, we kept the intervention modules brief (about 20-30 minutes each).

Module	Module's Goals	Session Content in Brief

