BL, 4, 12, 24	Potential Mediators	Work-Related Attitudes Scale: Work Importance and Confidence Ruler
Therapy Session	Process	Audio-recorded Phone Calls
Week 8, 24	Process	Satisfaction with Counseling and with Websites (mailed assessment)
End-of-Study	Process	Extent of Study Participation from Therapist Cell-Phone (# minutes on phone with Therapist) Extent of Benefits Counseling Website Use (# days logged on to website, # modules completed)
End-of-Study	Extract Data from C&P Exam and VA Database	Mental Health Diagnoses and service connection outcome and award determination from C&P Examination Reports and VBA databases and VA Mental Health Service Use from VA Databases

Justification for Schedule of Assessments: The initial 4-week assessment follow-up date was chosen because results of Motivational Interviewing interventions have been detectable this quickly in other studies [56]. In our randomized clinical trial of in-person Benefits Counseling, week 24 assessments allowed for detection of later emerging effects of Benefits Counseling.

Baseline Assessment Measures to Characterize Participants: The following measures will be administered by the Research Assistant in a face-to-face meeting prior to beginning the intervention:

1. Baseline Characteristics Questionnaire: A questionnaire to characterize study participants has been used in our recently-completed Benefits Counseling study. It covers the following domains: demographics, military history, psychiatric history, employment, legal status, and last 28 days of income by source. It also includes 10 items from the Attitudes toward Seeking Professional Psychological Help Scale-Short Form [57]. This widely-used scale consists of two factors, one reflecting openness to seeking treatment for emotional problems and the other reflecting value of seeking treatment and need for it. The Questionnaire also includes a four-question screen for TBI, a screen which is intended to be sensitive but not specific, when a single positive answer is interpreted as a positive screen [58]. Internet usage is measured using items derived from a clinical trial of an interactive voice response system [59]. Veterans are asked whether they own different technology types (e.g. a working cell phone), whether they make different uses of it (e-mail, text messaging, searching) and number of days engaged in activities such as sending e-mail.

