does not record how long was spent on the website because it cannot distinguish between when someone is using the program, has left the browser open, or has left the program without logging out. Study therapists will complete a contact log for each encounter. The contact log will document whether there was a scheduled contact that was not attended, the date and time of contact, and time spent in minutes.

End of Study Measures

1. The current diagnoses, service-connection outcome, and award determination will be obtained from the completed Compensation and Pension examination and VBA database. Diagnoses will be coded within DSM-V with specifiers for definite diagnoses and rule-outs.
2. VA Service Use Outcomes. Analyses will be conducted by [name], a national authority on service use analyses. Episodes reflecting use of VA substance abuse, specialized PTSD and other mental health treatment will be collected from VA administrative records as described previously [73, 74]. Information will be accessed by an agreement between the MIRECC and the West Haven-sited Northeast Program Evaluation Center (NEPEC), which routinely accesses this information for VA reports. VA bed section codes indicate hospitalization on specialized units and VA clinic codes indicate outpatient treatment in specialized clinics. Mental Health service use data will be collected from 24 weeks before the Compensation examination (to allow analyses to control for baseline service use) until 24 weeks after claims adjudication.
3. Cost of Therapist Time Providing the Intervention: The direct costs of providing Remotely-Delivered Benefits Counseling will be calculated but a full cost-effectiveness analysis is beyond the scope of this proposal. The amount of time the therapist spends will be calculated by having therapists maintain logs of time spent on study-related activities including conducting telephone calls, scheduling phone calls, and reminding Veterans to access the study website. The product of the therapist's time spent and the average therapist cost will be used to calculate the labor cost. Therapist salaries will be calculated including fringe benefits but not the overhead rate of the VA facilities. We will not include research costs, facility costs, or the costs of developing the intervention.

Data Analysis

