The general potential *mediators* of treatment response will include ratings of importance/confidence in ability to work, work-benefits attitudes (attitudes about one's personal situation, understanding of work-benefits relationship), service-connection award, and number of weeks engaged in any mental health and/or substance abuse treatment.

5. Evaluation of Process Measures: The Likert-scaled therapy process ratings and other measures reflecting single values (e.g. number of times logging into the study website) will be compared between groups using parametric or non-parametric group comparisons. Only the Benefits

Counseling group will have ratings of audiotaped therapy sessions and these will be tabulated for descriptive statistics.

6. Evaluation of Factors Associated with Effects of Study Treatments on Working (Moderators)

To determine what factors are associated with response to counseling, potential predictor variables will be serially entered into the primary outcome analyses as separate covariates, and as terms interacting with group-assignment. To avoid finding significant associations by chance, potential predictors will be screened for their intercorrelations with each other and redundant measures (e.g., $r > .7$; $R^2 \geq .6$; $VIF \geq 2.5$) will be pared or combined. Potential predictor variables include:

- Demographic variables (age, race, gender),
- Conditions that Make Working More Difficult: Substance use severity, baseline PTSD severity as measured by the PCL-5, overall psychological symptomatology as measured by the BSI, depression as measured by the BSI.
- Attitudes Toward Seeking Professional Psychological Help Scale-Short Form (two domains---openness to seeking treatment for emotional problems and value of seeking treatment).
- Veterans' rated reasons for seeking compensation as described by the Disability Application Appraisal and Inventory [28]: we hypothesize that Veterans who rate themselves higher in having applied for financial gain will be more likely to work in response to Benefits Counseling.

7. Evaluation of factors associated with progress through different steps of study participation

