2. Becoming upset while discussing traumatic events: There is a risk that individual Veterans will become upset by discussing their traumatic events during assessments or counseling. In practice, study-related adverse events in clinical trials involving PTSD assessments among Veterans have been very rare. Research assistants will emphasize that answering questions is voluntary and will allow Veterans to answer questions at their own pace and without duress.

3. Information from the counseling being told to participants' clinicians at the VA or to someone who reviews their disability application. The counseling is unlikely to impact the Veteran's disability application. The therapist will not volunteer any non-emergent information in the Veterans' chart or to other clinicians, as this is contrary to the voluntary, Motivational Interviewing stance that is integral to Benefits Counseling. The therapist will write a note in the Veteran's VA chart after any phone counseling indicating that the participant was in this research study and spoke to the therapist.

Nevertheless, the therapist is going to convey information to other VA clinicians if the Veteran indicates information during the therapy that requires emergency intervention. If the Veteran indicates information suggesting imminent danger to the Veteran or to others, the Benefits Counseling therapist will share this information with other VA clinicians so they can take appropriate action. Therefore, Veterans will be told the risk that information that they tell the study therapist may be told to their VA clinicians and would then become available to someone who reviews their disability application. It is very unlikely that an emergency disclosure would prevent receipt of service-connected disability.

4. Potential effect of work on the benefits application process: Veterans compensated for physical or mental problems that developed during or were made worse by military service are not supposed to be penalized for coping well with these problems by working. However, the Veterans Benefits Administration reviews claims on a case-by-case basis, and it is unknown to what extent working will influence any individual Veteran's disability determination process. Veterans will be told this as part of the informed consent process.

5. Breach of Confidentiality: The website will not contain any PHI.

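### Service-connection award is extracted at end of study with no date limit, so awards decided after week 24 may be counted as mediators of hours already worked

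*Combined protocol and SAP*

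**What the plan says.** - **Source and timing of the award.** End of Study Measures, item 1: "The current diagnoses, service-connection outcome, and award determination will be obtained from the completed Compensation and Pension examination and VBA database". The Schedule of Assessments has the same item in its End-of-Study rows, as "service connection outcome and award determination from C&P Examination Reports and VBA databases". Neither place gives a week, a latest decision date or a code for a claim still pending.
- **Use of the award.** Data Analysis, section 4, includes among the potential mediators "service-connection award, and number of weeks engaged in any mental health and/or substance abuse treatment". Each mediator's slope is to be related to group and to the slope of hours worked. It is then held constant in the partial correlation of group with that slope.
- **Outcome window.** Research plan, section A, places the last telephone assessment at week 24, and the Purpose section describes a 24-week trial.
- **Pending decisions.** Section B.1.d, on the third session: "If the C&P decision has not been received, the therapist will call again at 16 and 20 weeks".
- **Direction of influence.** Human Subjects, B.4: "it is unknown to what extent working will influence any individual Veteran's disability determination process".
- **Adjudication date.** End of Study Measures, item 2, collects mental health service use "until 24 weeks after claims adjudication".

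**The concern.** A mediator has to come before the outcome it explains. An award decided after the last work assessment cannot have changed hours that were already worked and recorded. Under the text as it stands, such an award would be scored the same as one made early in follow-up.

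Two errors could follow in the award-hours association. If awards do affect work, late awards add Veterans whose work could not have been affected, and the association is diluted. If work affects awards, late awards bring in an association that runs from hours to award, and it would be read as the opposite. In this population those are opposite conclusions: that awards discourage work, or that working lowers the chance of an award. An undated award variable cannot separate them.

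**Working it through.** The plan states no figure on this point, so the check is first one of time order and then an illustration of size.

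**Time order**
1. Hours are observed to week 24 and not beyond.
2. The award is read from records at end of study, with no limit tied to week 24.
3. The therapist's checks at weeks 12, 16 and 20 show that decisions are expected to be outstanding for some Veterans well into follow-up. No check after week 20 is described.
4. Nothing in the mediator section uses a decision date. The plan as written can therefore count an award decided after week 24.

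**Size: inputs.** From the plan: 104 Veterans with at least one follow-up assessment, and an expected group difference of 0.40 SD in slope. Assumed, because the documents are silent: half of the claims awarded; a share q decided after week 24 of 10%, 25% or 50%; and the effect sizes below. Out of 104, q = 10% is about 10 Veterans and q = 50% is 52.

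**Dilution.** Suppose timely awards change the hours slope by -0.50 SD and late awards cannot. Among Veterans ever awarded, a fraction 1 - q carries the effect, so the observed difference is -0.50 x (1 - q):
- q = 10%: -0.50 x 0.90 = -0.45
- q = 25%: -0.50 x 0.75 = -0.375
- q = 50%: -0.50 x 0.50 = -0.25

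Simulation gives -0.45, -0.37 to -0.38, and -0.25.

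**False association.** Suppose awards have no effect on hours, but each SD of hours slope lowers the log-odds of a late award by 0.5. With half awarded, the difference in mean slope (awarded minus not) among late decisions is -4 x 0.5 x E[p(1 - p)]. Here p is the award probability and E[p(1 - p)] = 0.236 for a standard normal slope, which gives -0.472. Over all Veterans the difference is -0.472 x q: -0.047, -0.118 and -0.236 at the three shares. For scale, the standard error of a half-and-half comparison in 104 Veterans is sqrt(4/104) = 0.196 SD, so these are about 0.2 to 1.2 standard errors.

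**Partial correlation of group with hours.** With the 0.40 SD group effect and the same reverse influence, the plain correlation is about 0.196. After controlling for award it is 0.196 at q = 10% and 0.194 at q = 50%. Doubling the log-odds to 1.0 at q = 50% moves it only from 0.194 to 0.190.

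**Would one cut-off date be enough?** Suppose work affects all awards, early and late, at log-odds 0.5. The false difference is then about -0.47 SD (-0.49 when the group effect is included), whether or not late decisions are dropped. A decision at week 20 also follows the baseline, week 4 and week 12 hours, which help form the slope.

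**The case against.** The best defense is that the problem may be small or absent. The documents do not say that any claim will be decided after week 24. Section B.1.d is conditional, and the third module is meant to follow the decision within the trial. Baseline may also take place up to three months after the examination, so a claim can be well advanced at randomization. This stands: the size is unknown, and it is zero if every decision arrives in time.

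It is also fair that the award is outside Hypotheses 2A and 2B, that the plan disclaims full mediation analysis, and that a one-time award has no slope, so the stated method does not fit it as written. These points lower the severity. They do not supply a date rule.

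A reader might infer more than the documents support:
- **That the award look-up must run past week 24 because service use is followed beyond adjudication.** That window governs service use only. It shows that an adjudication date is needed, not when the award is read.
- **That early entrants get a much longer look-up than late entrants.** This needs a single trial-level extraction. End-of-Study is undefined and sits in the visit column beside per-participant items such as modules completed. Neither reading gives a cut-off, and the point does not depend on which is meant.
- **That controlling for a late award distorts the treatment association.** The partial correlation hardly changes under the assumptions tried.

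**Conclusion.** The point holds as a gap in time order. The plan sets no limit that keeps awards decided after week 24 out of a mediator analysis of hours up to week 24, and it leaves the reverse path open. The possible damage is to the award-hours association: dilution of a -0.50 SD difference to between -0.45 and -0.25 SD, or a false difference of -0.05 to -0.24 SD. These figures rest on assumed late shares of 10% to 50%, half of claims awarded, and assumed effect sizes. The false-difference range also assumes that work influences late awards only.

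The primary slope comparison and the sample size are unaffected, and the partial correlation of group with hours is essentially so. Severity is minor: the award is one exploratory mediator outside the stated hypotheses.

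**What to change.** In End of Study Measures, item 1, record the decision date with the award. In Data Analysis, section 4, replace the single award value with a time-varying status (awarded, denied or pending) as of the start of each work-calendar period, and relate it only to hours in that period. Count decisions made after the last period began as pending, and report them descriptively.

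The SAP should state the calendar periods. If each covers the 28 days before its assessment, the follow-up periods open at weeks 0, 8 and 20 (4 - 4, 12 - 4 and 24 - 4). A claim decided at week 18 would then be pending for the first two periods and decided for the third. One decided at week 22 would be pending throughout. A single cut-off week applied to the whole slope should not be used instead, for the reason shown in the last step of the check.

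This ordering stops hours in a period from influencing the award status used for that period. It does not remove influence from earlier hours, so the result should still be reported as an association.

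The cost is SAP wording and one date per Veteran, which the service-use window already requires. Fewer Veterans will count as awarded or denied, so this exploratory analysis loses some precision. No visit, sample size or primary analysis changes.
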